8.0 SAFETY REPORTING

All study staff will prioritize participant safety while carrying out their day-to-day roles and responsibilities. Potential safety issues requiring follow-up, treatment, and/or referral may be identified through study-related activities, including:

- Clinical evaluations: Clinical staff (nurses, medical officers) may identify medical issues requiring follow-up, treatment, and/or referral when performing protocolspecified clinical assessments, as well as when reviewing study laboratory test results.
- Laboratory evaluations: The Medical Officers will be responsible for identifying laboratory test results requiring follow-up, treatment, and/or referral when performing protocol-specified tests.
- Questionnaires: Study staff, both clinical and non-clinical, may identify medical, drug adherence and/or psychosocial issues requiring follow-up, treatment, and/or referral when administering questionnaires to participants.
- Counselling: Study staff, both clinical and non-clinical, may identify medical, drug adherence and/or psychosocial issues requiring follow-up, treatment, and/or referral when providing counseling.
- Retention Activities: Study staff, both clinical and non-clinical, may identify medical and/or psychosocial issues requiring follow-up, treatment, and/or referral when conducting participant retention activities (e.g., visit reminders, locator contacts, and other outreach).

8.1 Safety Follow-up Procedures: Medical

In accordance with their training, qualifications, and designated study responsibilities, clinical staff will assess potential medical safety issues and identify medically appropriate follow-up, treatment, and/or referral requirements.

All follow-up actions, including diagnosis, treatment, and referrals, will be documented in chart notes.

- Medical emergencies will be managed per the site Clinical Emergency Treatment and Evacuation SOP
- Other medical issues will be managed per usual standards of care for medical practice in the study site locale.
- When appropriate and applicable, clinical staff will perform additional procedures to diagnose and treat medical problems. Additional (interim) study visits will be scheduled as needed to ensure timely follow-up. All visits, procedures, findings, and actions taken will be documented in chart notes.
- When medical issues are beyond the scope of services that can be provided through the study, clinical staff will actively refer participants to appropriate non-study health care providers for further evaluation and treatment.

All medical issues will be followed to resolution or stabilization, with the current status and further action plans (if applicable) documented at each study visit until resolution or stabilization occurs. All referrals will also be documented. At each study visit after a referral is made, the attending medical officer will actively follow-up on the referral to determine whether the participant sought the services to which the child was referred, determine the outcome of the referral, and determine whether additional referrals are needed. All follow-up actions, outcomes, and plans for next steps will be documented in chart notes.

- In the event that medical issues are reported during a study visit to non-clinical study staff members, these staff members will communicate the information to clinical staff during the visit so that clinical staff may assess the participant's report and proceed as described above.
- In the event that medical issues are reported to non-clinical study staff off-site (e.g., during outreach activities), these staff members will communicate the information either upon return to the clinic or by phone to the clinical/study co-ordinator who will determine the appropriate course of follow-up action.

8.2 Safety Follow-up Procedures: Psychosocial

In accordance with their training, qualifications, and designated study responsibilities, study staff will assess potential psychosocial safety issues and identify appropriate follow-up, treatment, and/or referral requirements.

All follow-up actions, including diagnosis, treatment, and referrals, will be documented in chart notes. Psychosocial emergencies will be referred to the Medical Out-Patients Department (MOPD) of the hospital on whose premises our CRS is located. Other nonemergency psychosocial issues will be managed per usual standards of care for medical practice in the study site locale.

- When appropriate and applicable, study staff will provide information and counselling to assist participants with addressing the issues. All such counselling will be documented in chart notes. Should the participant require more intense counselling or intervention strategies, they will be referred to the local hospital psychologist.
- When psychosocial issues are beyond the scope of services that can be provided through the study, study staff will actively refer participants to appropriate non-study service providers for further evaluation and assistance.

All psychosocial issues will be followed to resolution or stabilization, with the current status and further action plans (if applicable) documented at each study visit until resolution or stabilization occurs.

All referrals will also be documented. At each study visit after a referral is made, the attending medical officer will actively follow up on the referral to determine whether the mother of the participant sought the services to which the participant was referred, determine the outcome of the referral, and determine whether additional referrals are needed. All follow-up actions, outcomes, and plans for next steps will be documented in chart notes.

- In the event that psychosocial issues are reported during a study visit to study staff who are not trained/qualified to respond to the issues, these staff members will communicate the information to the clinical/study co-ordinator during the visit so that an appropriately trained staff member can assess the participant's report and proceed as described above.
- In the event that psychosocial issues are reported to study staff who are not trained/qualified to respond to the issues off-site (e.g., during outreach activities), these staff members will communicate the information — either upon return to the clinic or by phone — to the clinical/ study co-ordinator who will determine the appropriate course of follow-up action.

8.3 Documentation

Study-staff will document all safety-related participant reports (histories), observations, findings, and actions taken in response to these. In the event that study participants are hospitalized or otherwise treated by a non-study health care provider, every effort will be made to obtain copies of relevant medical records. These records will be copied and certified by the study receptionist. The clinical/study co-ordinator will oversee these efforts and all efforts will be documented in chart notes.

8.4 Internal and External Reporting

- Individual study staff members will routinely communicate participant safety information to their supervisors on a day-to-day basis. Specific case management will be discussed as needed in regular staff meetings as well as in individual staff supervision sessions and will be documented in meeting notes or minutes.
- Participant safety information, including any unanticipated problems related to study participation, will be reported to the South African Medicines Control Council and UKZN BREC.
- Related specifically to adverse event reporting:
- Event evaluation Case report forms (CRFs) will be completed per instructions on the case report form. Medical Officers will complete these CRFs.

8.5 Definitions

Adverse Event:

An adverse event (AE) is defined as any untoward medical occurrence in a clinical research participant administered an investigational product and which may or may not have a causal relationship with the investigational product. As such, an AE can be an unfavorable or unintended sign (including an abnormal laboratory finding, for example), symptom or disease temporally associated with the use of an investigational product, whether or not considered related to the product. Study participants will be instructed to contact the study clinician to report any AEs their infants may experience.

Serious Adverse Event:

A serious adverse event (SAE) is any untoward medical occurrence that at any dose that results in death, is life threatening, requires inpatient hospitalization or prolongation of existing hospitalization, results in persistent or significant disability/incapacity, or is a

congenital anomaly/birth defect (April 1996 International Conference on Harmonisation (ICH), Good Clinical Practice: Consolidated Guidance, (ICH E6). Important medical events that may not be immediately life – threatening or result in death or hospitalization but may jeopardize the patient or may require intervention to prevent one of the outcomes listed in the definition above may also be considered to be serious. (October 1994 ICH guidance (E2A), Clinical Safety Data Management: Definitions and Standards for Expedited Reporting).

SUSAR: Suspected, Unexpected Serious Adverse Reaction:

Serious (see SAE definition above)

Related (i.e. there is a reasonable possibility that the AE may be related to the study agent)

Unexpected (see definition below)

Unexpected AE:

An AE, the nature or severity (intensity) of which is not consistent with the applicable agent information (Investigator's Brochure, package insert, or summary of agent characteristics).

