To explore the safety of Truvada when used as PrEP in combination with current recommendations for prevention of sexually transmitted infections and HIV in young women at substantial risk of HIV acquisition during pregnancy and lactation.

2.2 Primary Objective:

 To compare the frequency and seriousness of specific adverse events related to TDF/FTC in women and their children in Arm A (exposure to TDF/FTC) and Arm B (no exposure to TDF/FTC) during pregnancy until breastfeeding cessation.

2.3 Secondary Objectives:

- To estimate HIV incidence in women in ARM A with ARM B at delivery and at 18 months post-delivery.
- To determine the interdependency of adherence to a once daily oral TDF/FTC regimen and standard HIV prevention methods during pregnancy and postdelivery.
- To measure antiretroviral drug (TDF/FTC) level in women and their infants in association with adherence, safety and level of protection (plasma and breastmilk)
- To detect drug resistance among women who acquire HIV infection and correlate the treatment outcomes (after initiating immediate ARV treatment) with drug resistance
- To determine mother-to-child transmission of HIV among women who acquire incident infections during pregnancy and breastfeeding and the frequency of drug resistance in their infected babies

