7.2 Cohort Accrual and Follow-up

Cohort accrual is expected to be completed in 12 months. Accrual to this study will be monitored by the Protocol Team in accordance with standard operating procedures. An overview of the study procedures for women and their infants are provided in Appendices 5 and 6. The women will follow the basic antenatal care schedule. For participants with early antenatal booking (<12 weeks), return visits will be scheduled for 20, 26-28, 32-34, and 38 weeks until delivery. Following delivery and a <72 hour postdelivery assessment women and their infants will be seen at 6, 10, 14 weeks and thereafter 4 weekly until 18 months postdelivery.

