7.13 Followup Visits for Infants

Infants will be assessed at birth, 26 weeks, 50 weeks and 74 weeks. In addition to a full physical examination, a blood sample will be drawn for assessing renal function (Creatinine Clearance) and Hormonal growth factors. For infants exposed to TDF/FTC an additional blood sample will be collected for a drug level assessment. At each visit the following growth parameters will be recorded: weight, height and head circumference. Infant feeding modality will be recorded at each visit. Cessation of breastfeeding is defined as 28 days after last exposure to breastmilk.

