10. STATISTICAL CONSIDERATIONS

10.1 Method of Randomisation

Enrolled participants will be assigned at random, to one of the two study treatment arms in equal proportions. The randomisation list used to assign individual study participants to one of the two treatment arms will be generated by the protocol statistician, using randomly permuted blocks. The randomisation statistician will provide the study pharmacy with sealed, opaque randomisation envelopes, sequentially labelled by PID. These envelopes will be assigned in sequential order to eligible study participants. Upon opening the envelope the pharmacist will add her name and signature as well as the time and date the envelope was opened. This being an open label study, the treatment assignment of a participant will be known by the participant and the study staff.

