10.2 Outcome Measures

Main Outcome Measure:

 Renal Function estimated by Serum Creatinine Clearance, adverse pregnancy outcomes (e.g., stillbirth, preterm delivery at < 37 weeks gestation, low birth weight <2,500 grams, and congenital anomalies) and Bone Mineral Density among women

Bone Mineral Density and growth parameters in neonates and infants until cessation of breastfeeding.

Other Outcome Measures:

- Confirmed presence of HIV infection detected by HIV NAT positivity at scheduled 3 monthly visits until 18 months.
- Adherence -self reported use of study product and pill count
- Partners HIV status at enrollment confirmed by Two POC tests and Adherence measured at delivery and 18 months postdelivery
- Antiretroviral drug level in plasma as a marker of adherence.
- Presence of viral resistance mutations that have been selected by Truvada (K65R, M184V) in participants who acquire HIV infection
- Mother to child transmission-reactive NAT testing performed in children born to mothers who acquire HIV infection during pregnancy and post-delivery.

Behavioural Risk:

- Number of sexual partners with whom participant had unprotected intercourse during pregnancy and postnatally
- Number of protected and unprotected acts of intercourse during pregnancy and postnatally
- Sexually transmitted infections acquired during pregnancy
- Sexually transmitted infections acquired postnatally
- Facilitators and barriers to adherence.

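### Infant illnesses that come and go between scheduled examinations have no stated, arm-symmetric solicitation in this open-label trial, so the Fisher comparison of adverse event counts is open to differential reporting for those events.

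*Combined protocol and SAP*

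**What the plan says.** Section 2.2 sets the primary objective: "To compare the frequency and seriousness of specific adverse events related to TDF/FTC in women and their children in Arm A" against Arm B, from pregnancy until breastfeeding ends. Section 10.4 counts adverse events in pregnancy and after delivery, splits them by seriousness and compares the arms with Fisher's exact test. Its restatement of the objective includes the newborn.

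On how infant events reach the data, 8.5 says: "Study participants will be instructed to contact the study clinician to report any AEs their infants may experience". On follow-up, 7.13 says: "Infants will be assessed at birth, 26 weeks, 50 weeks and 74 weeks". On content it says: "In addition to a full physical examination, a blood sample will be drawn for assessing renal function (Creatinine Clearance) and Hormonal growth factors", and it adds growth measurements and feeding mode. Section 7.2 gives a denser contact schedule: "women and their infants will be seen at 6, 10, 14 weeks and thereafter 4 weekly until 18 months postdelivery". On masking, 10.1 says: "This being an open label study, the treatment assignment of a participant will be known by the participant and the study staff". The child outcomes named as main outcomes in 10.2 are "Bone Mineral Density and growth parameters in neonates and infants until cessation of breastfeeding".

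**The concern.** A count of adverse events depends on how events are found as well as on how many occur. If one arm is asked and the other is not, or if both rely on mothers who know whether their infant is exposed, the recorded counts can differ when the true rates do not. Equally, a real difference can be hidden. The documents give no basis for predicting the direction: a mother in Arm A could report more than one in Arm B, or less, and unmasked staff could probe more in one arm.

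The stake is the child part of the adverse event comparison in 10.4. The protocol itself says that long-term breastmilk exposure to the drug needs study. A short illness that nobody asked about and that left no trace at the next examination cannot be fully recovered at analysis.

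**Working it through.** **1. Which provisions could capture an infant event, and whom they cover**

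| Place | What it provides | Infants named? | Same in both arms as written? |
|---|---|---|---|
| 8.5 | Mother contacts the clinician | Yes | Yes, but spontaneous |
| 7.21, opening questions | Asks about admissions, significant illness and side effects | No; asks participants about themselves | No; timed from starting Truvada |
| 7.12 | Adverse event assessment with toxicity grading, through week 74 | No subject named | Unclear; headed as visits during product use |
| 7.10 | Assessment of mother and child before discharge | Yes | Yes |
| 7.13, 7.21, Appendix 6 | Examination, growth, milestones, DXA, bloods | Yes | Yes in 7.13 and Appendix 6; 7.21 words the infant bloods for exposed infants |
| 8.1, 8.3 | Staff may identify and follow up issues; outside records are sought | In part | Yes, once staff know of the event |

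No row gives a stated history of infant illness since the last visit, asked of every mother in both arms.

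**2. How long the gaps are**

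On the 7.13 schedule the gaps after week 26 are 50 − 26 = 24 and 74 − 50 = 24 weeks. Section 7.21 adds growth and milestone checks at 6 weeks and 3 months, so the earlier gaps are shorter. On the 4-weekly schedule of 7.2 there are 24/4 − 1 = 5 mother-infant contacts inside each 24-week gap. None has a stated infant question.

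**3. The plan's own figure**

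The sample size rests on preterm delivery. With 18.5% in both arms, a margin of 7.5 points, two-sided 5% and 80% power:

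n = (1.960 + 0.842)² × 2 × 0.185 × 0.815 / 0.075² = 421 per arm.

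This matches 10.3. Preterm delivery is recorded by staff, so this point does not touch the calculation.

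**4. Illustration of size, on assumed values only**

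Observed proportion = true proportion of infants with at least one event × probability that it is reported. Assumed: 400 infants per arm, Fisher's exact test, two-sided 5%, rejection probabilities by exact enumeration.

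| True risk A v B | Reported A v B | Observed A v B | Test rejects |
|---|---|---|---|
| 40% v 40% | 60% v 60% | 24% v 24% | 4% |
| 40% v 40% | 70% v 60% | 28% v 24% | 23% |
| 40% v 40% | 80% v 60% | 32% v 24% | 69% |
| 40% v 30% | all | 40% v 30% | 83% |
| 40% v 30% | 60% v 70% | 24% v 21% | 15% |

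Range, at 421 per arm by normal approximation with equal true risks of 20%, 40% and 60%:
- Reporting of 90% v 80% gives spurious differences of 2, 4 and 6 points, and false significance in about 12%, 23% and 41%.
- Reporting of 80% v 60% gives 4, 8 and 12 points, and about 39%, 74% and 94%.

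These figures treat every infant event as dependent on the mother's report, which is an upper case. If only a share s of the affected infants have events of that kind, the spurious difference is roughly true risk × s × reporting gap. At 40% risk and a 10-point gap it is 4 points for s = 1, 0.40 × 0.5 × 0.10 = 2 points for s = 0.5, and 1 point for s = 0.25. The documents do not give s.

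**The case against.** The strongest case on the other side is that much infant safety data needs no report from the mother. Staff assess the child before discharge. Infants have scheduled examinations, bloods, DXA and growth checks, and 8.5 counts an abnormal laboratory finding as an adverse event. The child main outcomes in 10.2 are measured, and birth outcomes come from staff and the maternity record. The objective concerns specific events related to the drug, not every childhood illness. Appendix 5 has no adverse event row either, although 7.12 requires an assessment, so silence in Appendix 6 proves little. The case report forms are not in the documents and may contain the question.

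Most of this stands, and it rules out three stronger readings that a reader might infer:
- That infant events are recorded only if the mother makes contact. Section 8.5 does not say so, and the scheduled assessments are another route.
- That the whole child side of the primary comparison depends on who reports. The measured and staff-recorded outcomes do not.
- That 7.12 is confined to the woman. It names no subject.

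It does not close the gap. An examination up to 24 weeks later will not show a resolved illness unless someone asks. The staff identification in 8.0 is permissive. Retrieval of hospital records under 8.3 helps with serious events, but only after staff learn of them. The 4-weekly contacts lessen the problem in practice and make it easy to solve, but they carry no stated infant question.

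**Conclusion.** The point holds for one class of event: infant clinical events that arise and resolve between scheduled examinations. For these, the only infant-specific instruction is spontaneous contact by a mother who knows her arm. The active provisions in 7.12 and 7.21 do not name infants and are tied to the drug. The Fisher comparison of adverse event counts in 10.4 is open to differential reporting to that extent. Bone density, growth, laboratory and birth outcomes are not affected by it, and neither is the sample size.

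The size of the bias cannot be derived from the documents, which give neither an infant event rate nor a reporting probability. The figure of about 23% false positives is an illustration. It assumes 40% true risk, 400 infants per arm, 70% v 60% reporting, and that all the counted events depend on the mother's report. The direction is also unknown. This is a clear and cheap improvement to make, not a defect that undermines the trial's main outcomes.

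**What to change.** In 7.12, 7.13 and 8.5, and as a row in Appendix 6, state that every mother in both arms is asked the same scripted questions about her infant at every scheduled postnatal mother-infant visit, regardless of product use. The questions cover any illness, clinic attendance or admission since the last visit. Grade the answers on the same scale as maternal events.

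In 10.4, base the between-arm comparison of infant clinical events on these solicited records together with events found at scheduled examinations and laboratory tests. List spontaneous reports separately.

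Because that comparison would use laboratory findings, two related texts must be reconciled. Section 7.21 words the infant safety bloods for exposed infants, while Appendix 6 lists them for HIV-unexposed infants without regard to arm. The last infant visit is week 74 in 7.13 but week 72 in 7.21 and Appendix 6.

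The cost is one case report form page at visits that already take place about every 4 weeks, plus protocol wording. No visit or procedure is added. Scripted questions put to an unmasked mother reduce reporting bias but do not remove it, and the report should say so.

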9. QUALITY MANAGEMENT

The Quality Management plan includes both Quality assurance (QA) and Quality Control (QC)

9.1 **Quality Assurance**

QA involves periodic, systematic objective review of trial related activities to ensure that the trial is performed and the data are generated, documented and reported in compliance with good clinical practice (GCP).

The Clinical/study co-ordinator, medical officers and the Investigator will routinely review random selections of participant charts to ensure that protocol specifications related to participant safety are being followed and that appropriate clinical and psychosocial management is being provided and properly documented. The clinical/study co-ordinator, medical officers including the investigator will also review the charts of all participants experiencing serious and other expedited adverse events on a monthly basis to ensure proper management and documentation. If at any time these reviews identify areas for improvement, the clinical/study co-ordinator will follow-up with relevant study staff to ensure that any oversight or deficiency is appropriately addressed. All actions taken will be documented (e.g. in meeting minutes or training records).

